Title: The efficacy of ultrasound guided glenohumeral joint injections of platelet rich plasma (PRP) versus hyaluronic acid (HA) in the treatment of glenohumeral osteoarthritis: A randomized, double-blind control trial

NCT: 02984228

Document date: October 28, 2021

Title: The efficacy of ultrasound guided glenohumeral joint injections of platelet rich plasma (PRP) versus hyaluronic acid (HA) in the treatment of glenohumeral osteoarthritis: A randomized, double-blind control trial

Principal Investigator: [name]

Condition or Intervention to be studied: Treatment of glenohumeral osteoarthritis (OA) with a single injection of hyaluronic acid (HA) or platelet-rich plasma (PRP).

Research questions/specific aims: This study aimed to determine whether HA or PRP can decrease pain, restore function, and improve disability in patients suffering from chronic glenohumeral OA (both primary and secondary) that is refractory to conservative management (including corticosteroid injections).

Hypothesis: PRP injections are more efficacious than HA injections in patients with chronic glenohumeral OA.

Primary outcome: Shoulder Pain and Disability Index (SPADI) score, assessed at baseline and up to 52 weeks post-injection

Secondary outcomes:

1. American Shoulder and Elbow Surgeons Society Standardized Shoulder Assessment Form (ASES; assessed at baseline and up to 52 weeks post-injection)
2. Current numerical rating scale pain score (assessed at baseline and up to 52 weeks post-injection)
3. Average numerical rating scale pain score (assessed at baseline and up to 52 weeks post-injection)
4. Patient satisfaction (assessed up to 52 weeks post-injection)
5. Side effects (assessed up to 52 weeks post-injection)

Background:

Shoulder pain is common, making up 16% of all musculoskeletal complaints,^{1,2,3} with a lifetime prevalence as high as 50%.^{4,5,6} It is second only to low back pain in musculoskeletal disorders that present to primary care physicians.^{7,8} It has a high societal burden, contributing to decreased productivity and worker related disability,^{4,6,9-11} with direct costs of 7 billion US dollars reported in the year 2000.³ The management and course of patients who present with shoulder pain to a primary care physician is concerning, with only 50% reporting full resolution in 6 months, increasing to only 60% after 1 year.¹¹⁻¹⁴ Causes of shoulder pain include glenohumeral osteoarthritis, subacromial bursitis, trauma, rotator cuff tear, instability, adhesive capsulitis, or labral pathology. Risk factors include advanced age, history of trauma or instability, rheumatoid arthritis, female sex, and occupations or sports involving repetitive movements of the upper extremity.

Glenohumeral OA involves degeneration of the glenoid and humeral articular surfaces, associated with osteophyte formation, subchondral bony changes, and synovitis.¹⁵ It accounts for approximately 2-5% of all chronic shoulder pain and has an increased risk among the elderly,

patients with a history of glenohumeral subluxation, and those who participate in sports such as swimming, tennis, baseball, or volleyball.³ It may be classified into primary and secondary forms. Primary glenohumeral OA causes include degenerative joint disease, inflammatory arthropathies such as rheumatoid arthritis, septic arthritis, rotator cuff tear arthropathy (CTA), and neuropathic arthropathy secondary to syringomyelia or diabetes.¹⁶⁻¹⁸ Secondary causes include trauma, postoperative changes after arthroscopy or capsulography, and osteonecrosis due to underlying systemic problems such as chronic steroid or alcohol exposure.¹⁶

Hyaluronic acid (HA), or hyaluronate, is a high molecular weight glycosaminoglycan, found in synovial joint fluid, with viscoelastic, chondroprotective, and possible anti-inflammatory properties.¹⁹ The purpose of injecting the substance intrarticularly is to promote endogenous hyaluronic acid growth and production, which in turn increases joint lubrication and thus, decreases mechanical stress of the affected joint.²⁰ Taken as a whole, a number of studies show that at least a total of 3 weekly HA injections to either the subacromial space or glenohumeral joint, when compared to no control group or placebo improved pain and range of motion for 3 to 6 months.²⁰⁻²⁵ However, there continues to be inconsistency in the literature in terms of recruitment, sample size, injection technique, whether or not image guidance was used, and what type of hyaluronate was used.

Platelet rich plasma (PRP) injections involve the use of a patient's own platelets to take advantage of autologous blood growth factors present to promote tissue regeneration. It is more widely used for the treatment of tendinopathies and popular among injured athletes,²⁶ but is beginning to see potential use in the treatment of osteoarthritis.^{27,28} Existing research has suggested benefit in pain related to knee and hip osteoarthritis, but limited to no data is available for its effect on chronic glenohumeral osteoarthritis (both primary and secondary).²⁹⁻³²

To our knowledge, no study in the literature has been conducted that compares the efficacy of ultrasound guided PRP and HA injections with ultrasound guidance in the treatment of chronic glenohumeral arthroses.

References

2. van der Windt DA, Koes BW, de Jong BA, Bouter LM. Shoulder disorders in general practice: incidence, patient characteristics, and management. *Ann Rheum Dis.* 1995;54(12):959-964.
4. van der Windt DA, et al. Occupational risk factors for shoulder pain: a systematic review. *Occup Environ Med.* 2000 Jul;57(7):433-42.

31. Patel S, et al. Treatment With Platelet-Rich Plasma Is More Effective Than Placebo for Knee Osteoarthritis: A Prospective, Double-Blind, Randomized Trial. *The American Journal of Sports Medicine*. 2013;41(2):356-64.

Study design: Randomized controlled trial

Enrollment target: 70

Inclusion criteria:

1. English speaking/literate
2. Age 18-100 years
3. $\geq 5/10$ visual analog scale pain as a direct result of primary or secondary glenohumeral OA
4. At least 3 months of pain after onset of symptoms that has failed conservative treatments, including corticosteroid steroid injection (must be 3 months after corticosteroid injection)
5. Pre-procedure imaging of the affected glenohumeral joint
6. Transient relief of symptoms after diagnostic intra-articular injection into the glenohumeral joint

Exclusion criteria:

1. Painful active, concurrent cervical spine conditions
2. Current NSAID use (can be held for study)
3. History of taking Coumadin or similar anticoagulant, have a known coagulopathy, bleeding dyscrasia, or platelet count $< 150,000/\text{mm}^3$
4. Allergic reaction to poultry or previous viscosupplementation
5. Involved in workers' compensation or active litigation involving affected shoulder
6. Inability to refrain from NSAID use for 5 days prior to and 6 weeks after injection
7. History of corticosteroid injection to affected shoulder within the last 3 months
8. History of viscosupplementation or PRP to affected shoulder within the last 6 months
9. Presence of acute fracture
10. History of shoulder tumor
11. Known uncontrolled systematic illness (uncontrolled diabetes, HIV, vasculitis, autoimmune/inflammatory disease)
12. Psychiatric and somatoform disorders

Study procedures:

1. Patients will be randomized in a 1:1 fashion to the ultrasound-guided glenohumeral HA alone or PRP injection treatment group. Prior to injection, patients will be asked to discontinue any anti-inflammatory medications for 5 days prior to treatment.
 - a. HA group will receive one 6 mL injection of low molecular weight (average 500,000-730,000 dalton) HA preparation, Hyalgan (Fidia Farmaceutici S.p.A., Abano Terme, Italy). Needle guidance and injection will be performed under ultrasound to the affected glenohumeral joint, posterior approach, by a fellowship-trained physician. The syringe will be covered with an opaque shield to blind both the patient and treating physician.
 - b. PRP group will undergo the same above procedure as the HA group in respect to ultrasound guidance, anatomic approach, and double blinding. The Harvest Technologies Corporation (Plymouth, MA) SmartPReP Clear PRP preparation kit and machine will be used to prepare the samples in accordance with manufacturer

instructions. Venipuncture and blood collection, PRP centrifuge, final PRP preparation, and covering of the syringe with an opaque shield will be performed in a sterile manner by a trained study team member not involved in the direct care and management of the study subjects. Final PRP samples will aim to be leukocyte reduced. Prior to injection, each sample in the PRP group will be sent to the laboratory for hemoglobin / hematocrit, WBC, and platelet counts. 6 mL PRP will be injected.

2. In order to ensure that the treating physician is blinded to the treatment study subjects receive, the treating physician will perform ultrasound guidance and needle placement, but an Interventional Spine and Sports Medicine fellow or a Physiatry attending not involved in the study will prepare and perform the actual injection.
3. Post procedure:
 - a. Patients will be instructed to take acetaminophen 500 mg every 6 hours (maximum of 3 gms) for pain relief as needed.
 - b. Ice applied over the affected joint will not be allowed for 3 days and NSAIDs are to be avoided for at least 6 weeks after the intervention is performed due to their anti-inflammatory properties.
 - c. Patients will be instructed to avoid taking baths and swimming in order to minimize risk of infection. Showers are allowed. Patients can continue their usual activities of daily living, as tolerated.
 - d. Follow-up questionnaires will be administered at 1, 2, 3, 6, and 12 months post-injection.

Sample size analysis and statistical analysis plan:

Proposed analysis: Two-way repeated measures ANOVA

Alpha level: 0.05

Beta or power level: 0.861

Primary outcome variable estimate: SPADI

Number of groups being compared: 2

Effect size or change expected between groups: 10-point change (± 15)

Resulting number per group: 30

Total sample size required: 70

Descriptive analyses of the patient population will include reporting means (with standard deviations) for continuous variables and frequencies (with percentages) for discrete variables. Prior to initiation of inferential analyses, data will be evaluated for completeness and, for continuous measures, normality. Comparative differences between the study groups will be evaluated using independent samples t-test for continuous variables and chi-square/Fisher's exact test for categorical variables. This will include comparisons of patient characteristics as well as baseline patient reported outcomes and all range of motion measures. Factors that do not meet the assumption of normality will be analyzed using the non-parametric equivalents.

The primary outcome in this study is the total SPADI score and the longitudinal assessment of that score over four follow-up time points after baseline. A systematic review by Roy et al

(Arthritis Rheum, 2009) found that the minimal clinical important difference (MCID) for patients with general shoulder pain ranged between 8 and 13 points. Williams et al. (J Rheumatol, 1995) found that changes in the SPADI score between +10 and -10 points were not able to distinguish between shoulder patients whose condition improved, remained the same, or worsened. In a similarly designed study looking at the effect of intra-articular corticosteroids and supervised physiotherapy, Carette et al. (Arthritis & Rheumatism, 2003) used a 10-point change as their MCID. Given those estimates, we calculated our sample size based on the ability to detect a similar 10-point change between treatment groups in the total SPADI scores.

Group sample sizes of 25 patients in each treatment group of the study will achieve 86% power to detect an MCID of 10 points in the total SPADI score between groups with an estimated standard deviation of ± 15 points in a two-way repeated measures ANOVA design with statistical significance set to alpha equal to 0.05. To adjust for any loss of patients due to early withdrawal, we will increase our sample size by 20% for group sample sizes of 30 and a total sample size of 70 patients. All analyses will be based on an intent-to-treat model, and any missing data will be imputed using a last observation carried forward methodology. Mixed models will also be generated to adjust for any effects of potential confounding from age, sex, and other factors. Longitudinal assessment of the other patient reported outcomes will also be evaluated using similar statistical models.

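### The primary SPADI analysis covers four follow-up points but five are scheduled; the primary visits are therefore undefined, and the stated 86% power cannot be tied to one design.

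*Combined protocol and SAP*

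**What the plan says.** The section on sample size and statistical analysis takes total SPADI as the primary outcome, with "longitudinal assessment of that score over four follow-up time points after baseline". It does not name the four points. Study procedures, item 3d, reads: "Follow-up questionnaires will be administered at 1, 2, 3, 6, and 12 months post-injection". That is five visits. The front-page outcome entry does not decide between them: "Shoulder Pain and Disability Index (SPADI) score, assessed at baseline and up to 52 weeks post-injection".

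On power, the summary list gives "Proposed analysis: Two-way repeated measures ANOVA", "Alpha level: 0.05" and "Beta or power level: 0.861". The narrative adds "Group sample sizes of 25 patients in each treatment group of the study will achieve 86% power"; the target is a 10-point difference between the arms, with an SD of 15. The power statement does not give the number of measurements, the correlation between a patient's measurements, whether baseline counts as one of the occasions, or whether the group effect or the group-by-time interaction is tested.

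**The concern.** The visits that enter the model are part of the definition of the primary outcome. Read literally, the SAP drops one scheduled assessment without naming it. Dropping month 1 and dropping month 12 give different summaries, since one loses early response and the other loses durability. If the choice is not fixed in advance, it can be made with results in view. Missing values are to be filled by last observation carried forward, so the visit list also decides which values are carried and to where.

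The number of measurements is also an input to any repeated measures power calculation. When the count is in doubt and the other inputs are missing, a reader cannot tell which design the 86% describes.

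**Working it through.** **Inputs from the documents.** 25 evaluable patients per group, difference δ = 10, SD = 15 (variance 225), alpha 0.05, target power 0.861.

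**Assumptions.** Two-sided test. Equal correlation ρ between all of a patient's measurements; no value is given, so a range is shown.

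**Step 1: single time point.** SE = √(2 × 225/25) = 4.243 and 10/4.243 = 2.357. Power = Φ(2.357 − 1.960) = 0.654, or 0.637 by t-test. One-sided versions give 0.762 and 0.751. None is 0.861, so the stated figure relies on repeated measurements.

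**Step 2: group difference averaged over k measurements.** The variance factor is f = (1 + (k − 1)ρ)/k and SE = √(2 × 225 × f/25). The normal approximation is Φ(δ/SE − 1.960). The ANOVA between-group F test has 1 and 48 df and noncentrality (25/2) × δ²/(225 × f).

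At ρ = 0.5:
- k = 5: f = 0.600, SE = 3.286, 10/3.286 = 3.043, power Φ(1.083) = 0.861. The F test gives 0.847.
- k = 4: f = 0.625, SE = 3.354, 10/3.354 = 2.981, power Φ(1.021) = 0.846. The F test gives 0.832.

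So five measurements at ρ = 0.5 reproduce 0.861 by normal approximation, but other combinations do so too.

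**Step 3: correlation needed for exactly 0.861.**

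| Follow-ups averaged | Normal approximation | F test |
|---|---|---|
| 4 | 0.466 | 0.434 |
| 5 | 0.499 | 0.469 |

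With ρ fixed at 0.434, going from four to five follow-ups moves the F-test power from 0.861 to 0.878. With ρ fixed at 0.469, going from five to four moves it from 0.861 to 0.845. The visit count alone is worth about 1.4 to 1.7 points across the two methods. Correlation matters far more: from ρ = 0.3 to 0.7 the F-test power falls from 0.918 to 0.747 (k = 4) and from 0.936 to 0.755 (k = 5).

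**Step 4: baseline as an outcome level, group main effect tested.** Randomisation makes the expected baseline difference zero, so the averaged difference shrinks. At ρ = 0.5:
- Baseline plus four: δ = 10 × 4/5 = 8, SE = 3.286 (k = 5), 8/3.286 = 2.434, power Φ(0.474) = 0.68. The F test gives 0.66.
- Baseline plus five: δ = 10 × 5/6 = 8.33, f = 0.583, SE = 3.240 (k = 6), 8.33/3.240 = 2.572, power Φ(0.612) = 0.73. The F test gives 0.71.

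Even this design can reach 0.861 if ρ is low: baseline plus five does so at ρ of about 0.30 (normal approximation).

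**Step 5: group-by-time interaction.** With a difference of 0 at baseline and 10 at every follow-up, and ρ = 0.5, power is 0.645 (four follow-ups) or 0.626 (five). About 0.86 needs ρ just under 0.7.

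**Step 6: baseline as a covariate.** The variance factor becomes f − ρ². At ρ = 0.5 it is 0.625 − 0.25 = 0.375 for four follow-ups, or 0.600 − 0.25 = 0.35 for five. Power is 0.97 or 0.98 by normal approximation.

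**The case against.** The strongest reply is that this is a slip in one word with little numerical effect. Four versus five follow-ups changes power by under 2 points, and a longitudinal model over several visits is usually less sensitive to losing one visit than a single-time-point analysis is to the choice of its time point. Both statements are fair. They limit the size of the problem, but they do not say which visits are primary.

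Two stronger readings are tempting, and the documents support neither.

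- A reader might infer that 86% holds only if all five measurements are post-injection, because five measurements at correlation 0.5 give 0.861. That correlation is not in the documents, and the match appears only under the normal approximation; the F test gives 0.847. Four follow-ups give 0.861 at a slightly lower correlation.
- A reader might infer that the calculation assumes a 10-point difference at baseline, or that true power is 68%. That would require baseline to be an outcome level and the group main effect to be the tested term. The plan states neither. The lower figures show what that reading would cost, not what the plan does.

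It can also be said that the documents do not show which count is the error, and that making baseline a covariate specifies the model further instead of correcting a count. Both points stand. The fix therefore leaves room for a justified omission and offers the covariate as the way to settle baseline's role.

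**Conclusion.** The contradiction over the visit count is certain: both statements are current text, and nothing else in the document resolves it. The primary visit set is undefined and should be fixed before results are examined.

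The power finding is narrower. The 86% is not shown to be wrong and is attainable with either visit count at moderate correlations. It cannot be verified or assigned to one design, mainly because the correlation and the tested term are missing; the visit count is a minor part. The material exposure is conditional: about 66% to 73% if baseline is an outcome level and the group main effect is tested, or about 63% to 64% for the interaction. Both assume equal correlation of 0.5, SD 15, 25 per group, a constant 10-point difference at every follow-up and a two-sided 0.05 test. This should be corrected, but it does not invalidate the design.

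**What to change.** Reconcile Study procedures item 3d with the primary outcome paragraph of the SAP:

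1. List the visits in the primary model: months 1, 2, 3, 6 and 12, unless the sponsor gives a reason to omit a named one.
2. State that baseline SPADI enters as a covariate and not as an outcome occasion.
3. Name the tested contrast, for example the group difference averaged over the listed visits or the difference at a named visit.
4. Restate the power with the number of post-injection measurements, the assumed correlation and the test used.

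If outcome data have already been examined, report all five visits and say openly when the set was chosen.

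The cost is a few sentences and one rerun of the power calculation, with no extra patients or visits. Baseline adjustment would raise power, not lower it: for the average over follow-ups it is about 97% to 98% at an assumed correlation of 0.5.

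### The repeated measures ANOVA for SPADI is named, but not the term or contrast that decides PRP versus HA; the 86% power carries no correlation, and baseline SPADI is not named as a covariate

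*Combined protocol and SAP*

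**What the plan says.** The section on sample size and statistical analysis gives "Proposed analysis: Two-way repeated measures ANOVA", alpha 0.05 and "Beta or power level: 0.861". Its closing paragraph states that "Group sample sizes of 25 patients in each treatment group of the study will achieve 86% power to detect an MCID of 10 points" in total SPADI, "with an estimated standard deviation of ± 15 points in a two-way repeated measures ANOVA design". The 25 is then raised by 20%: "To adjust for any loss of patients due to early withdrawal", the groups become 30 and the total is given as 70.

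The front summary has "Primary outcome: Shoulder Pain and Disability Index (SPADI) score, assessed at baseline and up to 52 weeks post-injection", so baseline sits inside the primary outcome. The analysis section describes a longitudinal assessment over four follow-ups after baseline, whereas Study procedures, item 3d, has "Follow-up questionnaires will be administered at 1, 2, 3, 6, and 12 months post-injection", which is five.

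The closing paragraph also says "Mixed models will also be generated to adjust for any effects of potential confounding from age, sex, and other factors". It does not rank these models against the ANOVA. The only stated use of baseline patient-reported outcomes is a comparison between the groups. All analyses are intent-to-treat, with last observation carried forward for missing data.

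**The concern.** A two-way repeated measures ANOVA produces two tests that can show a treatment difference: group, and group by time. The plan names neither as primary, and names no visit or average of visits. It does not say whether baseline is a level of the time factor, which changes what both tests measure. It gives no within-patient correlation, and does not say whether 15 is the SD of a single score or of a change.

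The line of output that decides the trial could therefore be chosen after the data are seen, and the lines differ widely in power under the plan's own inputs. The plan also passes over an inexpensive gain: baseline SPADI is collected, and adjusting for it would raise power without more patients.

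**Working it through.** **Inputs from the documents:** n = 25 per group, difference 10, SD 15, alpha 0.05 (taken as two-sided), and k = 5 follow-ups (Study procedures) or 4 (analysis section).

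**Assumptions:** compound symmetry with correlation ρ from 0.3 to 0.8 (not in the documents), 10 points at every follow-up and none at baseline, and 15 as the single-visit SD unless stated otherwise.

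**Reproducing the 86%.** One visit alone gives 65.4% (normal approximation) or 63.7% (noncentral t), so the figure is not a single-visit test. For the group effect over five follow-ups at ρ = 0.5:
- Variance of a patient's mean = 225(1 + 4×0.5)/5 = 135, so the SD is 11.62.
- Standard error of the difference = 11.62×√(2/25) = 3.286.
- 10/3.286 = 3.043, less 1.960 = 1.083, giving 86.1% by normal approximation. Noncentral t with 48 df gives 84.6%.

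If 15 is the SD of change and mean change is tested, the variance is 112.5(1 + 1/5) = 135 at any ρ, so the result is the same. The stated figure can thus be matched, but only by supplying a term and, if 15 is a single-visit SD, a correlation.

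**Other readings, k = 5, ρ = 0.5:**
- Group effect with baseline as a level: difference 10×5/6 = 8.33, variance 225(1 + 5×0.5)/6 = 131.25, power 71.2%.
- Group by time with baseline as a level: noncentrality (25/2)×100×(5/6)/(225×0.5) = 9.26, df 5 and 240, power 62.6%.
- Group by time over follow-ups only: a constant difference leaves no interaction, so power equals alpha, 5%.
- Baseline-adjusted mean of follow-ups: variance 225(1 − ρ)(1/5 + ρ) = 225×0.5×0.7 = 78.75, 47 df, power 97.4%.

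**Across the correlation range (k = 5, 25 per group):**

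| Test | ρ 0.3 | ρ 0.5 | ρ 0.7 | ρ 0.8 |
|---|---|---|---|---|
| Group, follow-ups only | 94% | 85% | 75% | 71% |
| Group, baseline as a level | 85% | 71% | 60% | 56% |
| Group by time, baseline as a level | 46% | 63% | 87% | 97% |
| Baseline-adjusted mean | 97% | 97% | 99% | >99% |

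Group by time reaches 86.1% at ρ of about 0.69. With four follow-ups and ρ = 0.5, the rows are 83.2, 66.5, 64.5 and 96.5%, so the four-versus-five discrepancy moves the follow-up group effect by about 1.5 points.

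**Lowest power of the adjusted mean.** Its variance is largest at ρ = 0.40: 225×0.6×0.6 = 81, power 97.0%. Allowing for chance baseline imbalance, this becomes about 96.7%.

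**If 15 is the SD of change.** The adjusted variance is 112.5(1/5 + ρ): 78.75, 101.25 and 112.5 at ρ = 0.5, 0.7 and 0.8. Power is 97, 93 and 90%, with a limit near 85% as ρ approaches 1.

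**Late-only effect.** With 10 points at months 6 and 12 only, the five-visit average is 2×10/5 = 4 points, and adjusted power is 35% at ρ = 0.5. Month 12 alone, adjusted for baseline, has variance 225(1 − ρ²): power 76% at ρ = 0.5 and 90% at 0.7, for 10 points at that visit.

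**Either ANOVA test counted as success.** The two tests are independent under compound symmetry, so type I error is 1 − 0.95² = 9.75%. Simulation gave about 9.6%.

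**The case against.** The plan describes its 10 points as a difference between the treatment groups, which leans towards the group effect, and that effect reproduces 86% almost exactly at ρ = 0.5. This stands as the likeliest reading. It does not say whether baseline is a level, which alone moves power from 85 to 71%, and it does not exclude a claim from the interaction.

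A reader might infer several stronger things that the documents do not support:
- **That the 86% is wrong, or holds for only one reading.** It is stated once, with no term and no correlation, so it is shown for no particular reading. Group by time also reaches it near ρ = 0.69.
- **That the trial would miss a true 10-point benefit in 35 to 37% of cases.** This is group by time at ρ = 0.5 with 25 analysed (100 − 64.5 and 100 − 62.6). At ρ = 0.7 that test has 87 to 88%. A total of 70 at 1:1 is 35 per group. If all 35 are analysed, as carrying observations forward could allow, group by time has 80 to 81% at ρ = 0.5, although imputation may dilute the effect. With 28 left after a 20% loss it has 69 to 70%.
- **That the false positive rate is 9.75%.** No passage says that success on either test suffices. The figure shows only what the ambiguity would permit.
- **That baseline SPADI is left out of every model.** The mixed models leave their further covariates open, so it is unnamed rather than excluded. Adjustment is a recommendation for efficiency; its absence is not an error.

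Averaging over visits is also a choice of estimand. Equal weights on months 1, 2, 3, 6 and 12 put 60% of the weight on the first three months. That objection stands and must be answered in the fix.

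**Conclusion.** The point holds in limited form and should be fixed. Outcome, method and alpha are set, but the deciding term or contrast is not, and neither the role of baseline nor the inputs behind 86% are stated. The size depends on the correlation. With 25 analysed per group, five follow-ups and a constant 10-point difference, the possible group tests run from 94 down to 56% over ρ 0.3 to 0.8, and group by time with baseline as a level from 46 up to 97%. A baseline-adjusted mean stays at about 96.5% or more if 15 is a single-visit SD. If 15 is the SD of change, that margin narrows to 90% at ρ = 0.8 and towards 85% beyond it. All these figures rest on compound symmetry and an assumed correlation. The documents do not show the trial to be underpowered or its error rate to be inflated.

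**What to change.** Make these changes before unblinded data are seen. The specific aims are already phrased in the past tense, so the plan should record when the change was made.

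1. Name one primary contrast: the PRP minus HA difference in mean total SPADI over the scheduled follow-ups, equally weighted, two-sided 0.05. Estimate it from a mixed model with treatment, visit, treatment by visit, baseline SPADI and baseline by visit. Baseline is a covariate and not an outcome level.
2. Make the ANOVA group and group-by-time tests, and the models adding age and sex, secondary.
3. Say whether the last-observation-carried-forward rule applies to this model.
4. Restate power with its assumptions: the number analysed, the number of visits, the correlation, and whether 15 is a single-visit SD (about 96.5% or more with 25 per group and five follow-ups) or the SD of change (about 97, 93 and 90% at ρ = 0.5, 0.7 and 0.8, limit near 85%).
5. State that averaging dilutes a late effect. If durability is the question, name month 12 as primary instead and accept about 76% at ρ = 0.5 or 90% at 0.7.
6. Reconcile the four follow-ups in the analysis section with the five in Study procedures.

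The cost is plan wording and one recomputation. Baseline SPADI is already collected and mixed models are already foreseen, so no patients or visits are added.

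### The stated total of 70 does not follow from 30 patients per group: two equal groups of 30 make 60

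*Combined protocol and SAP*

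**What the plan says.** The figures appear in three places in the combined protocol and SAP.

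- **Enrollment target** (under the study design): "Enrollment target: 70".
- **Study procedures, item 1**: "Patients will be randomized in a 1:1 fashion", to hyaluronic acid or platelet-rich plasma.
- **Sample size analysis and statistical analysis plan**. The summary list gives "Number of groups being compared: 2", then "Resulting number per group: 30" and "Total sample size required: 70". The closing paragraph begins "Group sample sizes of 25 patients in each treatment group of the study will achieve 86% power" and then makes its allowance for early withdrawal: "we will increase our sample size by 20% for group sample sizes of 30 and a total sample size of 70 patients".

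The pairing of 30 per group with 70 in total is therefore made twice, once in the list and once in a full sentence. The 70 is repeated as the enrollment target.

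**The concern.** With two groups and equal allocation, the total must be twice the group size. Here it is 10 more than that, and nothing in the document says where those 10 patients come from.

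The sample-size statement is the justification for how many patients receive an injection. As written, a reader cannot tell whether 30 or 35 patients per arm are planned, or how much withdrawal the plan was meant to absorb. Any later comparison of achieved with planned enrolment, or of observed with planned attrition, would carry the same ambiguity.

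**Working it through.** **Inputs**

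- Powered size: 25 per group (closing paragraph of the sample-size section).
- Increase for early withdrawal: 20% (same paragraph).
- Groups: 2 (summary list), randomised 1:1 (Study procedures, item 1).
- Stated results: 30 per group and 70 in total (summary list and closing paragraph); enrollment target 70.

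**Reproducing the plan's figures**

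1. Powered total: 2 × 25 = 50.
2. Per group after the increase: 25 × (1 + 0.20) = 30. This agrees with the plan.
3. Total after the increase: 2 × 30 = 60. The plan says 70, so the gap is 70 − 60 = 10 patients.

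**Working back from 70**

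4. Per group at 1:1: 70 / 2 = 35.
5. Increase over the powered total: 70 / 50 = 1.40, that is 40%.

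**Would another inflation formula give 70?**

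6. Suppose the 20% is read as an expected loss rate, so that n / (1 − d) applies. Per group, 25 / 0.80 = 31.25, rounded up to 32, and 2 × 32 = 64.
7. Inflating the total in one step gives 50 / 0.80 = 62.5, rounded up to 63.

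Neither gives 70, and step 6 would also contradict the stated 30 per group. Rounding cannot account for the difference.

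**What each reading allows for withdrawal**

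| Per group | Total | Increase over 50 | Losses that leave 25 per group |
|---|---|---|---|
| 30 | 60 | 20% | 5 of 30 = 16.7% |
| 35 | 70 | 40% | 10 of 35 = 28.6% |

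The last column counts completers. The SAP specifies an intent-to-treat analysis with last observation carried forward, so withdrawn patients stay in the analysis. The percentages describe the recruitment allowance and not the number analysed.

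**The case against.** The best case for the plan is that little depends on the slip. The number that governs recruitment is the same wherever it appears: 70 under the enrollment target, in the summary list and in the closing paragraph. It is larger than 50, than 60, and than the 64 from the stricter inflation formula, so no reading leaves the trial below its calculated size. The effect size, standard deviation, alpha, stated power and 25 per group are unaffected; only the last step, from group size to total, fails. All of this stands, and it limits the seriousness of the point. It does not make the figures agree.

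Three further objections bear on the remedy.

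- **The withdrawal rate.** The plan does tie its 20% to early withdrawal, so an allowance is given. But 20% is the amount added, which is not the same as a loss rate: a 20% loss from 30 leaves 30 × 0.80 = 24, one short of 25. The assumed loss rate still needs stating.
- **A rationale worked backwards.** The 40% increase is derived here from 70, and the sponsor gave no such basis. That is fair. It should go into the plan only if the sponsor confirms that 70 is intended, with the sponsor's own reason.
- **The standing of 25 per group.** The power for 25 per group rests on a repeated-measures design, and the document states no within-patient correlation. That is a separate question. This point takes 25 as given and does not vouch for it.

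**Conclusion.** The inconsistency is real: 30 per group in two equal groups is 60, and the plan says 70. The discrepancy is 10 patients, or equivalently an increase of 40% where 20% is stated. It is not an artefact of text extraction or redaction, because the same pair of figures appears in a list and again in a complete sentence.

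The conclusion rests only on two groups, 1:1 allocation and the plan's own numbers. The 63 and 64 in the working depend on the added assumption that 20% is a loss rate, and the finding does not need them. The documents do not show whether 60 or 70 was meant.

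This should be corrected, because the sample size is a core design figure and its derivation is wrong as written. It is not evidence of a shortfall in power.

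**What to change.** Reconcile the Enrollment target, the summary list and the closing paragraph of the sample-size section. State the assumed withdrawal rate and the basis for the total. Either of two corrections makes the figures consistent.

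- **If 70 is intended:** change 30 per group to 35 in the summary list and the closing paragraph, and replace the 20% increase with text such as: *a 40% increase, to 35 per group and 70 in total, which keeps 25 completers per group with up to 28% withdrawal* (35 × 0.72 = 25.2). Add the sponsor's reason for that allowance.
- **If the 20% increase is intended:** keep 30 per group and change the total, in both places, and the enrollment target to 60. The allowance then keeps 25 completers per group with up to 16% withdrawal (30 × 0.84 = 25.2).

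If the sponsor in fact expects 20% of patients to withdraw and wants 25 completers per group, the per-group figure is 32 and the total 64.

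Keeping 70 costs wording only and adds no patients to the existing target. Moving to 60 or 64 lowers the enrollment target and so changes the planned size of the trial. The document does not say how far enrolment has progressed, so the sponsor would need to check that before choosing a lower total.
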